## **Summary**

It is critical to evaluate strategies to leverage women's engagement in antenatal care to increase male partner testing. Secondary distribution of invitation letters for wellness visits from pregnant women to their male partners could be an innovative strategy to overcome barriers to men's reluctance to come to antenatal clinics for HIV testing. If men are motivated to attend ANC clinic's that offer a package of preventative health services, then the uptake and acceptability of testing for HIV at the clinic may improve as well. Increased proportions of men who test for HIV can then improve the number of men who link to HIV prevention and care services. For pregnant and postpartum women with HIV, partner testing and disclosure could facilitate women's continuation of ART post-partum. Thus, multiple public health goals could be achieved through increasing the proportion of men who know their HIV status.

## **STUDY METHODS**

### *Overall design*

This is a randomized factorial trial to assess two strategies; one to increase HIV testing and engagement  
Kingasa Study Protocol

in care among male partners of pregnant women, and the second to improving ART continuation and adherence among the HIV-positive pregnant women. The overall goal is to evaluate the impact of innovative strategies to increase male partner HIV testing, and engagement in HIV care and prevention among men and their pregnant partners, through ANC services provided to HIV- positive women.

We will recruit HIV-positive women with a partner of unknown HIV status through PMTCT B+ programs at Kitebi Health Center III in Kampala. Women will be randomized 1:1:1:1 to

- Arm 1: Women will be provided the standard of care invitation letter for male partners for fast-track visit for HIV testing and laboratory HIV testing at enrollment and every 6 months until 6 months postpartum,
- Arm 2: Women will be provided the standard of care invitation letter for male partners for fast-track visit for HIV testing and POC VL tests for women at enrollment, delivery, and 6 months post-partum;
- Arm 3: Women will be provided an invitation letter for male partners for wellness visits and laboratory-based HIV VL testing for women at enrollment, delivery, and 6 months post-partum;
- Arm 4: Women will be provided an invitation letter for male partners invitation letter for male partners for wellness visits and POC viral load testing for women at enrollment, delivery, and 6 months post-partum.

Women who are randomized to receive POC VL will receive same day ART adherence counseling and those randomized to receive lab based VL will receive VL results at their next visit with ART adherence counseling based on their VL results.

Male partners of women who are randomized to the wellness visit will receive a phone call from a male counselor after HIV testing to encourage linkage to care and prevention, depending on HIV status.

We will encourage men who test HIV-negative to use PrEP until their partner has achieved viral suppression (typically six months). However, all HIV-negative men will be offered PrEP, and men who test HIV- positive will be encouraged to start ART. Per recent Ugandan MOH guidelines, women in both arms will be provided HIVST kits for their partners with self-instruction materials about HIVST, encouragement to seek confirmatory testing and counseling, and brief educational materials about PrEP and ART, along with instruction in the use and interpretation of HIVST.

All women and men in the cohort will be screened for COVID-19 symptoms.

The primary endpoint of the randomized intervention for male partners is the proportion of male partners who test for HIV at the clinic, during the study. The primary analysis is an intent to treat comparison by randomization arms (comparing Arms 1 and 2 combined to Arms 3 and 4 combined) of the proportion achieving the primary outcome. The secondary outcome is engagement in care of the male partners, defined as 1) for HIV-negative men initiating PrEP within six months of randomization of their HIV-positive partner is randomized, and 2) for HIV-positive men, initiation of ART within 6 months after their HIV positive partner is randomized. Quantitative and qualitative methods will be used to assess acceptability of dual syphilis and HIV testing, blood pressure, visual acuity screening, and COVID-19 screening as part of wellness visits for male partners whose partner was randomized to the intervention arm, PrEP among male partners who test HIV negative, ART among male partners who test HIV positive, and identify ways to minimize social harms through antenatal programs that try to reach men.

The primary endpoint of the randomized intervention for pregnant women with HIV is viral suppression at 6 months post-partum. The primary analysis is an intent to treat comparison by randomization arm (arms 1 and 3 combined compared to arms 2 and 4 combined) of the primary outcome, of the proportion of women living with HIV who are virally suppressed at 6 months post-partum by arm, as the measure of continuation of ART and high adherence post-partum.

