#### Antenatal and postnatal care

Data collection will occur during standard of care antenatal/postnatal visits. HIV-positive pregnant women will access routine care at antenatal clinics according to guidelines for preventing and treating HIV infection in Uganda (64). Pregnant women will have up to 4 antenatal visits before delivery with 1 visit in the first trimester, 1 visit in the second trimester and 2 visits in the third trimester. The standard- of-care antenatal package includes cotrimoxazole preventive therapy, nutrition assessment, iron, folic acid and multivitamin supplementation and screening for syphilis. Women newly initiating ART in PMTCT B+ will have same-day pre-ART adherence counselling and ART initiation (Table 1). They will have PMTCT B+ follow-up

visit two weeks after initiating ART, and monthly visits for ART refills thereafter until delivery. Women will be offered delivery at a facility of their choice. Women randomized to the POC VL arm will receive POC VL testing at her delivery, as well as POC EID testing for her infant. After delivery, women will be followed quarterly for up to 6 months. Women in both arms will be screened for COVID-19 symptoms, and those with symptoms will be tested by SARS-CoV-2 PCR and those without symptoms will be screened for antibodies. Those who are PCR positive will be referred to a medical officer for clinical evaluation and contact tracing.

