Brief study questionnaires will be administered will occur at the PMTCT visits to avoid separate study-specific visits. Postnatal care and infant immunization visits will follow the routine maternal and child health (MCH) schedule. Viral load (VL) monitoring will include POC VL testing at enrollment, delivery, and every 6 months until M6 post-partum for women randomized to the intervention arm, and laboratory HIV RNA testing at enrollment, and every 6 months until M6 post-partum for women randomized to the control arm. Blood samples will be batch-tested at collaborating laboratories. Women will be asked about interruptions in ART use. If the mother is stable on ART with good adherence and undetectable VL, post-partum visits will be scheduled for week 6, and months 3 and 6. During these clinic visits, women will complete interviewer-administered surveys to collect data on behavioral factors that could mediate women's post-partum ART use. Women in the intervention arm will be provided their viral load results at that visit, and in the control arm will receive their viral load results at their next visit, in addition to counseling about the relationship between adherence, viral load and transmission risk.

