## Management of Viral Load Results

Participants in the intervention arm will have all routine ART monitoring tests performed according to the schedule described in the SoC arm follow-up procedures, however the POC VL assays will be utilized instead of lab based VL testing. POC VL testing will be performed using Cepheid's GeneXpert® HIV-1 VL assay performed at the beginning of the clinical encounter, so the clinical examination can be performed during the 90 minutes required to run a GeneXpert HIV VL test. If the participant is not able to wait for the results, then the study team will allow the participant to leave the study clinic but will ask them to remain in the vicinity and return to the clinic for their VL results. Prior to consent and enrollment, all potential participants will be counseled on the study procedures to ensure participants are able to comply with Intervention Arm study procedures, including potentially spending more time in clinic to receive VL results than they normally would as part of SoC clinic procedures. The GeneXpert testing will be conducted in the adjacent clinic site laboratory. Results will be managed according to SoC South African guidelines.

The clinical decisions from the SOC VL testing will adhere to the Ugandan guidelines. The algorithm for the current VL monitoring guidelines is summarized below:

- HIV VL <50 copies/mL: Reinforce the importance of good ART adherence and continue routine VL monitoring
- HIV VL 50-999 copies/mL: Provide standard of care ART adherence counseling, provide ART,

and ask participant to return to the clinic in six months for repeat VL testing. If the VL remains high (50-999 copies/mL) upon repeat testing, then the participant should continue receiving enhanced adherence counseling and repeat VL testing every six months until viral suppression (<50 copies/mL) is achieved.

- HIV VL  $\geq 1,000$  copies/mL: Provide standard of care ART adherence counseling; provide ART and ask participant to return to the clinic in three months for repeat VL testing. If the VL remains high ( $\geq 1,000$  copies/mL) after repeat testing, then participants will be considered for switching to second line treatment according to Uganda guidelines.

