**Table 5. Procedures for HIV-positive pregnant women**

	ANTENATAL				Delivery	POSTNATAL	
	T1	T2	T3	T4		M3	M6
ADMINISTRATIVE AND REGULATORY PROCEDURES							
Obtain written informed consent	[X]	[X]	[X]	[X]			
Assign participant identification number	[X]	[X]	[X]	[X]			
Assess eligibility	[X]	[X]	[X]	[X]			
Collect/update locator information	[X]	[X]	[X]	[X]		X	X
Collect/update demographic information	[X]	[X]	[X]	[X]			
Obtain random allocation	[X]	[X]	[X]	[X]			
Schedule next visit	[X]	[X]	[X]	[X]		X	X
COUNSELING							
HIV/STI risk reduction counseling, condom provision	[X]	[X]	[X]	[X]		X	X
Standard of care counseling (ART adherence, clinical & prevention benefits)	[X]	[X]	[X]	[X]		X	X
CLINICAL PROCEDURES							
Provide HIV test results	[X]	[X]	[X]	[X]			
Medical history	[X]	[X]	[X]	[X]		X	X
Perform physical exam	[X]	[X]	[X]	[X]		[X]	[X]
STI syndromic assessment and management	[X]	[X]	[X]	[X]		[X]	[X]
Referral for / provision of ART according to national guidelines	[X]	[X]	[X]	[X]		X	X
PMTCT PROCEDURES*							
Antenatal care package	[X]	[X]	[X]	[X]			
Postnatal care package						[X]	[X]
Infant HIV status at 6 weeks						X	
LABORATORY PROCEDURES							
Syphilis testing	X	[X]	[X]	[X]			
HIV serology	X	[X]	[X]	[X]			
Plasma HIV viral load (control arm)	[X]	[X]	[X]	[X]			X*
POC viral load (intervention arm) with same day ART adherence counseling	[X]	[X]	[X]	[X]	X		X

\*Standard of care

Study staff will perform study specific procedures at collaborating clinics

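### The protocol contradicts itself on whether laboratory viral-load women are tested at delivery, so the pooled Aim 2 control has no single stated schedule

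*Protocol*

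**What the plan says.** Arm numbers here follow the Overall design section, where Arms 1 and 3 have laboratory VL and Arms 2 and 4 have POC VL. Figure 3 and the list below it number the arms differently, which is a separate matter.

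- Overall design, Arm 1: "laboratory HIV testing at enrollment and every 6 months until 6 months postpartum".
- Overall design, Arm 3: "laboratory-based HIV VL testing for women at enrollment, delivery, and 6 months post-partum".
- Overall design, Arm 2: "POC VL tests for women at enrollment, delivery, and 6 months post-partum". Arm 4 has the same times.
- Antenatal and postnatal care, on delivery: "Women randomized to the POC VL arm will receive POC VL testing at her delivery". Nothing is said there about laboratory women.
- Antenatal and postnatal care, on VL monitoring: "POC VL testing at enrollment, delivery, and every 6 months until M6 post-partum for women randomized to the intervention arm", against "laboratory HIV RNA testing at enrollment, and every 6 months until M6 post-partum for women randomized to the control arm".
- Management of Viral Load Results: routine monitoring of POC women is done "according to the schedule described in the SoC arm follow-up procedures", with the POC assay replacing the laboratory one.
- Table 5: the row starting "Plasma HIV viral load (control arm" has an empty Delivery cell. The POC row has an X there.

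The primary Aim 2 analysis compares Arms 1 and 3 combined with Arms 2 and 4 combined on viral suppression at 6 months post-partum.

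**The concern.** In a 2x2 factorial, Arms 1 and 3 should differ only in the letter given to the male partner. The Overall design section makes them differ in VL monitoring as well, and these are the two arms pooled as the Aim 2 control.

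The Aim 2 endpoint is itself the month-6 VL, so only earlier VLs can influence it. Each VL leads to counseling based on the result: the same day for POC women, at the next visit for laboratory women. Under the Background heading on POC viral load, POC women above 200 c/ml receive additional counseling. In the algorithm for standard-of-care results, 1,000 copies/mL or more leads to a repeat test in three months. Whether a woman has a VL at delivery is therefore a difference in what she receives before the endpoint. Analysis cannot repair it if sites read the protocol differently.

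**Working it through.** **Step 1: the statements side by side.**

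| Place in the protocol | Laboratory women, VL at delivery | POC women, VL at delivery |
|---|---|---|
| Summary, arm description | Not named (6-monthly, to 12 months) | Not named (6-monthly, to 12 months) |
| Background, POC HIV Viral Load | Silent | Named |
| Overall design, Arm 1 | Not named | n/a |
| Overall design, Arm 3 | Named | n/a |
| Overall design, Arms 2 and 4 | n/a | Named |
| List below Figure 3 | No test times given | Named |
| Antenatal and postnatal care, delivery sentence | Silent | Named |
| Antenatal and postnatal care, VL monitoring sentence | Not named | Named |
| Table 5 | Cell empty | X |
| Management of Viral Load Results | Routine POC tests said to follow this schedule | Assay replaced only |

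No single schedule fits every row. If Arm 3 is right, the VL monitoring sentence and Table 5 are wrong for at least half of the control. If those two are right, the Arm 3 line is wrong and the same-schedule sentence needs qualification. The conflict stands in running prose, so it does not depend on how the table was extracted.

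**Step 2: how many women each reading affects.** 200 women at 1:1:1:1 give 50 per arm and 100 per pooled group.

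- Arm 3 line applied to Arm 3 only: 50 of 100 control women have a named delivery VL and 50 do not. The split coincides with the wellness letter.
- VL monitoring sentence and Table 5 applied: 0 of 100 control women and 100 of 100 POC women have one.

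**Step 3: the plan's own Aim 2 figures.** For two proportions with n = 100 per group and two-sided alpha 0.05, power = Φ{[Δ − 1.96·√(2p̄(1−p̄)/n)] / √([p₁(1−p₁)+p₂(1−p₂)]/n)}. For 70% against 86%, p̄ = 0.78, so (0.16 − 0.1148)/0.0575 = 0.786 and power is 78.4%. The other rows give 79.0% (60% to 78%) and 77.1% (80% to 93%). Solved for 80% power, the detectable differences are 18.2, 16.3 and 13.4 points, which round to the stated 18, 16 and 13. Those figures are not in dispute.

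**Step 4: an illustration resting on an assumption.** The documents give no effect for a delivery VL. Let f be the assumed share of the planned 16 points (70% row) that comes from the delivery VL and its counseling. Assume also that a laboratory delivery VL would confer that same share.

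- Arm 3 only also tested: difference = 16 × (1 − f/2).
- Both laboratory arms also tested: difference = 16 × (1 − f).

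| f | Arm 3 only: difference, power | Both laboratory arms: difference, power |
|---|---|---|
| 0.25 | 14 points, 68% | 12 points, 56% |
| 0.50 | 12 points, 56% | 8 points, 31% |
| 0.75 | 10 points, 44% | 4 points, 12% |

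This shows only that the choice of reading could matter. It does not estimate a bias.

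**The case against.** The strongest reply has four parts.

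**A POC-only delivery VL is openly described.** Several sections list it as part of the POC strategy, and it is paired with infant testing. Comparing a package with standard of care is a legitimate pragmatic design. This stands, but the Aim 2 statement names only POC testing and same-day counseling, and the Arm 3 line still contradicts that reading.

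**The Arm 3 line may be repeated wording.** It uses the same test times as Arms 2 and 4, and every other passage that sets laboratory test times omits delivery. A reader might infer that the pooled control is in fact mixed. The documents do not support that as a fact: it follows only if the Arm 3 line governs Arm 3 alone.

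**The number of earlier tests is not fixed.** A reader might infer from Table 5 that POC women have two VL-guided counseling occasions before the endpoint and laboratory women one. That is not a stated figure. The antenatal cells are bracketed in both rows, which the legend defines as conditional, and a 6-monthly test could fall near delivery for a woman enrolled early in pregnancy. High results also bring repeat tests. In addition, counseling is offered every 3 months to all, so any difference is one VL-informed session and not adherence counseling as such.

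**The same-schedule sentence covers routine monitoring.** A delivery test could be additional to that. This stands in part: the sentence is in tension with a POC-only delivery VL but is not plainly false.

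**Conclusion.** The inconsistency is real and concerns the control condition of a primary comparison. As written, the protocol does not say with one voice whether any, half or all of the 100 laboratory women have a delivery VL.

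Two consequences follow, each conditional on the reading:

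- If the Arm 3 line governs Arm 3 only, VL monitoring within the control is tied to the wellness-letter factor.
- If the VL monitoring sentence and Table 5 govern, the POC group may have an additional VL-guided counseling round before month 6. The Aim 2 effect could then not be attributed to POC testing and same-day results alone.

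The size of any bias cannot be taken from the documents, and the power range above rests wholly on the assumed f. The stated Aim 2 power figures reproduce. A reader might go further and conclude that the Aim 2 comparison is invalid. It is not: randomization still supports a comparison of the two strategies as delivered, provided that they are defined.

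**What to change.** Reconcile the Arm 1 and Arm 3 lines in Overall design, the VL monitoring text in Antenatal and postnatal care, the same-schedule sentence in Management of Viral Load Results, and Table 5, so that Arms 1 and 3 share one stated VL schedule. Which schedule that is remains for the investigators to decide; this review does not choose.

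If the laboratory schedule then differs from the POC schedule:

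- amend the same-schedule sentence to state the difference, but keep it, because it also says that the POC assay replaces the laboratory one;
- word the Aim 2 contrast and its conclusion as POC VL with same-day counseling, including a delivery VL, against standard-of-care laboratory VL.

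The cost is protocol wording. The downside is a narrower Aim 2 claim: it would concern the whole POC strategy and not the effect of faster results alone.

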## *Objectives*

**Aim 1: To determine the proportion of male partners of pregnant HIV-positive women who test for HIV at the clinic, based on invitation to a wellness visit (dual syphilis and HIV rapid test, blood pressure, visual acuity screening and COVID symptom screening, and if available, PCR testing for those with symptoms) compared to the standard of care (standard of care invitation letter for HIV fast track testing at the clinic).**

Innovations are needed to address the challenges associated with male partner engagement during their partner's antenatal and postpartum care periods. Provision of wellness visits providing STI testing and general health services, may overcome male partners reluctance to be tested in PMTCT clinics. We will randomize women 1:1 to the intervention and control arm and determine the proportion of male partners who test for HIV based on male enrollment numbers and data on HIV testing.

Primary outcome: The proportion of male partners who test for HIV compared by arms (comparing Arms 1 and 2 combined to Arms 3 and 4 combined).

**Aim 2: To evaluate whether POC viral load testing with same day ART adherence counseling improves ART continuation, and viral suppression among pregnant women living with HIV.**

Point-of-care viral load (POC VL) testing has been demonstrated to enable task-shifting and real-time adherence counseling. It is innovative to utilize POC VL for pregnant and post-partum women for real-time assessment of ART adherence, to improve ART use, retention in care, and viral suppression post-partum.

We will assess POC viral load monitoring and targeted ART adherence counseling compared to the standard of care laboratory-based HIV RNA testing, (comparing arms 1 and 3 combined to Arms 2 and 4 combined). Primary outcomes are viral suppression and HIV status disclosure at 6 months post-partum. *Hypotheses: POC viral load testing and same day adherence counseling will increase ART continuation and viral suppression*

Primary outcome: The proportion of HIV-positive women who are virally suppressed at 6 months post-partum. Viral suppression will be defined as plasma viral load <50 copies/ml.

**Aim 3: To evaluate whether engagement in care is improved among male partners who are provided a phone call follow up from a male counselor after HIV testing compared to standard of care.**

Pregnant HIV-positive women may be more likely to continue ART after delivery and have higher adherence post-partum if their partners are tested, there is mutual disclosure of HIV status, and their partner takes ART or PrEP, depending on his status. We will evaluate linkage to HIV treatment or care among all men enrolled in the study.

Engagement in care is defined as initiating PrEP for men who test HIV-negative and initiating ART for men who test HIV-positive, both within 6 months of their partner's randomization. Men who do not test are defined as not engaged in care.

Primary outcome: Proportion of HIV-negative male partners who initiate PrEP and HIV-positive men who initiate ART within 6 months across both arms. The secondary outcome will evaluate the proportions who initiate PrEP and ART by arm.

**Aim 4: To evaluate acceptability and preferences for HIV testing and other health services among men using qualitative methods.**

We will use quantitative and qualitative methods to assess acceptability and preferences for dual syphilis and HIV testing, blood pressure, visual acuity screening and COVID-19 testing among men attending wellness visits. We will assess acceptability and preferences of strategies to improve male partner testing, among female participants. Quantitative behavioral data will be collected from the study cohort during clinic visits using multiple validated questionnaires. Focus group discussions or in-depth interviews will be held with men who volunteer to join. These discussions will aim to achieve a better understanding of barriers and to motivators to seeking HIV care, testing for HIV, and acceptability of wellness visits.

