In the Kingasa study, we will use a factorial design in order to evaluate both an intervention to increase male partner HIV testing and an intervention for pregnant and postpartum women living with HIV to provide real-time HIV VL load and ART adherence counseling. Specifically, we will evaluate a) whether invitations to wellness visits increase the proportion of male partners who test for HIV and b) whether POC HIV VL tests increase viral suppression among pregnant and postpartum women living with HIV. We will also assess the impact of providing male counselor phone call follow-up to men in the wellness visit arm to encourage linkage to HIV care and prevention after HIV testing. Women will be randomized 1:1:1:1 to receive a) standard of care interventions with an invitation letter for male partners for fast-track visit for HIV testing and laboratory HIV testing for women at enrollment and every 6 months until 12 months postpartum, b) invitation letter for male partners for fast track visit for HIV testing and POC VL tests for women at enrollment and every 6 months until 12 months postpartum; c) invitation letter to male partners for wellness visits and laboratory-based HIV VL testing for women at enrollment and every 6 months until 12 months postpartum; and d) invitation letter to male partners for wellness visits and POC viral load testing for women at enrollment and every 6 months until 12 months post-partum. Women who are randomized to receive POC VL will receive same day ART adherence counseling and those randomized to receive lab based VL will receive VL results at their next visit with ART adherence counseling based on their VL results.

Women in both arms will receive counseling to minimize social harms associated with status disclosure and HIV testing, and additional counseling and referral to social support services when social harms occur. Based on the current Ugandan MOH guidelines to offer HIVST to both HIV-positive and HIV-negative pregnant women in ANC clinics, women in both arms will be provided an HIVST to give to their partner if they choose. They will be trained in the use and interpretation of the HIVST and be given information about HIV testing and prevention and care services, which she will give to her partner.

This study has been designed to address the gap in male partner engagement by using innovative methods to link men to HIV testing, prevention and care, and thus PMTCT outcomes for women.

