- Aim 3:** To assess the proportion of HIV-negative male partners who initiate PrEP and HIV positive men who initiate ART among male partners who test for HIV and are provided male counselor phone follow up or who receive standard of care.
- Aim 4:** To evaluate acceptability and preferences for HIV testing and other health services among pregnant women and male partners using mixed methods.

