Aim 3: The primary outcome is the proportion of HIV-negative male partners who initiate PrEP and HIV-positive men who initiate ART within 6 months across both arms. The secondary outcome will evaluate the proportions who initiate PrEP and ART by arm. The outcomes are engagement in care, defined as: 1) PrEP initiation among HIV negative men or 2) ART initiation among HIV positive men. PrEP use will be measured by pharmacy records where men are dispensed PrEP (e.g. at Kitebi clinic or IDI Kasangati), and self-report through a validated questionnaire. ART initiation will be assessed through pharmacy records.

Capture of cohort clinical data

Data on male partner HIV testing and female partner ART use and viral load will be obtained from case report forms. Clinic and pharmacy records will be used to document PrEP prescriptions, abstracted in real time from pharmacy records to paper-based case report forms and entered into an electronic database. Automated legal range checks will be programmed to reduce data entry errors and internal quality control reports will be run monthly.

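### Aim 3 is worded as a test of the male-counselor call, but its primary outcome is a proportion pooled across arms with conflicting denominators, and the by-arm contrast measures the whole wellness-arm package

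*Protocol*

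**What the plan says.** - **Question, comparative.** In Objectives, Aim 3 is "To evaluate whether engagement in care is improved among male partners who are provided a phone call follow up from a male counselor", with standard of care as comparator. The Summary says likewise: "We will also assess the impact of providing male counselor phone call follow-up to men in the wellness visit arm".
- **Question, descriptive.** The Aim 3 line that closes the Summary asks only for the proportions starting PrEP or ART, "among male partners who test for HIV and are provided male counselor phone follow up or who receive standard of care".
- **Primary outcome.** Objectives give "Proportion of HIV-negative male partners who initiate PrEP and HIV-positive men who initiate ART within 6 months across both arms". Outcome measurements repeat it: "The primary outcome is the proportion of HIV-negative male partners who initiate PrEP", with the matching ART proportion, again across both arms.
- **Secondary outcome.** "The secondary outcome will evaluate the proportions who initiate PrEP and ART by arm".
- **Denominator.** The Summary restricts to men who test. Objectives say "We will evaluate linkage to HIV treatment or care among all men enrolled in the study", then "Men who do not test are defined as not engaged in care". The second rule has work to do only if non-testers are counted.
- **Who is called.** The Summary and Overall design give the post-test call to partners of women randomized to the wellness visit, and to no one else.
- **Other male-staff contact.** Study Enrollment has women asked about phone contact by a male staff member, as standard of care and with no limit by arm. Male partner procedures describe such contact, with the woman's permission, for the intervention arm.
- **Rank.** Overall design makes engagement in care secondary to HIV testing for the male-partner randomization.

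**The concern.** Aims 1 and 2 each name the arms that their primary outcome compares. Aim 3 asks whether something improves, yet its primary outcome compares nothing. Three consequences follow.

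1. The primary result cannot answer the question as Objectives and the Summary narrative put it. The background justifies the call on the ground that it has not been systematically evaluated, and a pooled proportion would leave it so.
2. The size of the result depends on a denominator that the protocol states in different ways.
3. The result that does bear on the question, the by-arm one, could be reported as the effect of the call when it also carries the effect of the wellness invitation on testing.

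**Working it through.** The protocol states no effect size, power or sample size for Aim 3, so there is no figure to reproduce.

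**Inputs.** 200 women randomized 1:1:1:1, so 100 per side on the male-partner factor. Testing rates from the power section and Table 4: 20% vs 42%, 25% vs 46%, 30% vs 50%. The protocol gives no initiation rate for this trial, so r = 30-90% among testers is assumed. Tests are two-sided z-tests at 0.05 with pooled variance.

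**1. A pooled proportion carries no contrast.** Take 20 + 42 = 62 testers and a pooled 60%, which is 0.60 × 62 = 37.2 initiators. This fits:
- 60% vs 60% (no effect);
- 40% vs (37.2 − 8)/42 = 69.5% (benefit);
- 80% vs (37.2 − 16)/42 = 50.5% (harm).

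**2. Denominator.** Pooled result among testers divided by pooled result among all partners = 200 / number tested.

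| Testing, control vs wellness | Tested | Ratio |
|---|---|---|
| 20% vs 42% | 62 | 200/62 = 3.2 |
| 25% vs 46% | 71 | 200/71 = 2.8 |
| 30% vs 50% | 80 | 200/80 = 2.5 |

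The ratio needs no assumed r. At r = 70% the outcome is 70% among testers, or 0.70 × 62/200 = 21.7% to 0.70 × 80/200 = 28.0% among all partners. At the 45% tested across arms in the preceding study, the ratio is 1/0.45 = 2.2. Table 4 sets no six-month limit; fewer testers by month 6 would widen the gap. Men enrolled form much the same group as men who test, because enrollment is offered when a man comes to the clinic. The real divide is therefore between testers and all partners.

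**3. By-arm difference over all partners with no call effect.** With the same r in both arms, difference = r × (difference in testing).

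| Testing | r = 30% | r = 90% |
|---|---|---|
| 20% vs 42% | 6.0% vs 12.6%: 6.6 points, P(p<0.05) = 0.36 | 18.0% vs 37.8%: 19.8 points, 0.88 |
| 30% vs 50% | 9.0% vs 15.0%: 6.0 points, 0.26 | 27.0% vs 45.0%: 18.0 points, 0.76 |

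The effect on testing alone gives about 6 to 20 points and a 0.26-0.88 chance of a significant result.

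**4. By-arm difference among testers.** These groups form after randomization, through the event that the letter is meant to change. Points needed for 80% power:

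| Testers | Control 30% | 50% | 70% | 80% | 90% |
|---|---|---|---|---|---|
| 20 vs 42 | 37 | 34 | 26 | not reachable | not reachable |
| 25 vs 46 | 34 | 32 | 25 | 20 | not reachable |
| 30 vs 50 | 32 | 30 | 24 | 19 | not reachable |

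**5. Power of the all-partner contrast, 100 vs 100.** For 80% power, a control proportion of 6% needs about 13 points, 9% about 15, 18% about 17.5, and 27% about 19.

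**The case against.** The strongest reply is that Aim 3 is really descriptive. The Summary's aim is descriptive, the primary outcome in Objectives and Outcome measurements matches it, and the by-arm comparison is planned as secondary. On that view only the Objectives heading and one Summary sentence are out of line, and rewording them would end the contradiction. This stands as far as it goes: descriptive rewording is a legitimate repair. But it abandons the question that the Summary narrative poses and the background motivates, while a randomized contrast that addresses part of it is already planned.

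It may also be said that the denominator belongs in an analysis plan, and that outcomes worded for HIV-negative and HIV-positive men presuppose a test. The non-tester rule defines engagement and does not expressly set a denominator. That favors the testers reading but leaves the rule without a function, and a later plan that chose one reading would not remove the conflicting protocol text.

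Promoting the by-arm contrast has weaknesses: it partly restates Aim 1, and it can be significant with no call effect. Both are true, which is why the estimand must be named as the package.

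A reader might infer that tying the call to the wellness arms is itself a design error. The documents do not support this. The Summary and Overall design state the bundle openly, and a bundled intervention is legitimate. Only the wording that attributes the result to the call goes too far. Nor is the missing time anchor in Outcome measurements a contradiction, since Overall design and Objectives both count from the woman's randomization.

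**Conclusion.** The point holds. Aim 3 is worded both as a test of the call and as a description, and the pooled primary outcome can serve only the second. The testers and all-partner denominators differ 2.5- to 3.2-fold on the protocol's own testing rates. The by-arm result estimates everything the wellness arms receive, and would show about 6 to 20 points with no call effect. That last range rests on the assumed 30-90% initiation, equal in both arms, and on the power-section testing rates.

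A reader might infer that the trial's main conclusions are at risk, or that no comparison is planned for Aim 3. Neither follows. The power section covers only Aims 1 and 2, whose conclusions are untouched, and the by-arm comparison exists as a secondary outcome. The change should be made, but it is confined to Aim 3.

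**What to change.** - **Primary Aim 3 analysis.** Use the planned by-arm difference in PrEP or ART initiation within 6 months of the woman's randomization, wellness versus fast-track. Name the arms by content, because Figure 3 and the text after it number Arms 2 and 3 differently for the male-partner factor. Count the partners of all randomized women, with non-testers as not engaged.
- **Estimand.** Reword Aim 3 in Objectives and the matching Summary sentence as the effect of the full male-partner package: wellness invitation, post-test call, and any male-staff contact that differs by arm. Study Enrollment and Male partner procedures must first be reconciled on who receives that contact. State that the effect includes the effect on testing and supports no claim for the call alone.
- **Other results.** Report the pooled proportion as descriptive. Report the among-testers comparison by arm as supportive only, noting its selection after randomization.
- **Consistency.** Use one denominator in the Summary, Objectives and Outcome measurements. Engagement stays secondary to HIV testing for the male-partner randomization, as Overall design has it.

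**Cost.** A protocol amendment with ethics review; no new data, visits or procedures. The downsides are overlap with Aim 1 and limited power, with about 13 to 19 points needed for 80% power.
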